### **6.7.3 Definitions of DLT**

DLT will be defined as any of the following AEs that are considered possibly related to MLN9708. Toxicity will be assessed according to the CTCAE version 4.03.

1. Grade 4 neutropenia ( $ANC < 500/mm^3$ ) lasting more than 7 consecutive days.
2. Grade 3 or greater neutropenia ( $ANC < 1,000/mm^3$ ) with fever and/or infection, where fever is defined as axillary temperature  $\geq 38.0^\circ C$ .
3. Grade 4 thrombocytopenia (platelets  $< 25,000/mm^3$ ) lasting more than 7 consecutive days.
4. Grade 3 or greater thrombocytopenia ( $< 50,000/mm^3$ ) with clinically significant bleeding, or which requires blood transfusion.

5. A platelet count < 10,000/mm^3.
6. Grade 2 peripheral neuropathy with pain or Grade 3 or greater peripheral neuropathy.
7. Any other Grade 3 or greater nonhematologic toxicities with the following exceptions:
  - Grade 3 or greater arthralgia/myalgia.
  - Grade 3 or greater fatigue lasting less than 7 days.
  - Grade 3 nausea and/or emesis which can be controlled with anti-emetic therapies including anti-emetic prophylaxis. Anti-emetic prophylaxis is defined as an anti-emetic regimen that employs a 5-HT3 antagonist given in standard doses and according to standard schedules. Dexamethasone should not be administered as an anti-emetic.
  - Diarrhea that is controlled with appropriate supportive care
8. A delay of more than 14 days in the initiation of Cycle 2 treatment because of a lack of adequate recovery of MLN9708 related hematological or nonhematologic toxicities.
9. Other Grade 2 or greater MLN9708 related nonhematologic toxicities that, in the opinion of the investigator, require permanent discontinuation of MLN9708.
10. Inability to give at least 80% of the planned lenalidomide doses (Rd combination cohort only) due to the adverse events related to MLN9708.

When a subject experiences any of the above DLTs, MLN9708 therapy should be interrupted within the same cycle after DLT. With agreement by the sponsor, investigators may consider restarting the MLN9708 therapy from next cycle for subjects continue to clinically benefit from the therapy. MLN9708 should be reinitiated in accordance with “[6.4.3 Criteria for Dose Delays](#)”.

The sponsor will consult with the ESEC for the final decision if determination of DLT or subjects’ eligibility for DLT-assessment is difficult.

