### **3.3 Number of Subjects**

Approximately 12 to 24 subjects (3 to 6 subjects in each cohort) will be enrolled in the study.

If any significant protocol deviation that affects DLT assessment is observed or a subject could not complete the protocol-specified MLN9708 treatment during the DLT-assessment period for reasons other than DLTs, the subject will be excluded from the DLT assessment, and additional subject(s) may be enrolled. Moreover, if there seems to be needs for additional data for safety or pharmacokinetics evaluation, the sponsor may decide to enroll additional subjects. See “[10.2 Sample Size Considerations](#) for the sample size justification.

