## **6.3 Dosage, administration method, dosing schedule**

### **6.3.1 MLN9708 administration**

In this study, MLN9708 will be administered orally once weekly for 3 weeks (on Days 1, 8, and 15 and skip Day 22) in a 28-day cycle for up to 12 cycles.

MLN9708 will be taken on an empty stomach at least 1 hour before or no sooner than 2 hours after a meal.

In Cycle 1, MLN9708 will be given according to the dosage and administration specified in this study protocol; no interruption, delays, or reduction will be permitted.

Missed doses of MLN9708 in Cycle 2 and subsequent cycles can be taken as soon as the patient remembers provided that at least 3 days elapses between doses (until Day 4). If a patient vomits after taking MLN9708, the patient should not repeat the dose, but resume dosing at the time of the next schedule.

Once a dose is reduced, no re-escalation will be permitted.

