### 6.5.1.1.2 Dose Modification for Non-hematological Toxicity

If non-hematological toxicities shown in [Table 6-4](#) occur in Cycle 2 and subsequent cycles, MLN9708 should be interrupted. Upon recovery, MLN9708 may be reinitiated with one dose level reduction. For Grade 4 non-hematological toxicities, MLN9708 should be discontinued permanently.

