### **6.7.2 DLT-Evaluable Subjects**

DLT-evaluable subjects are defined as follows:

- DLTs  $\geq 1$  during DLT-assessment period.

OR

- Received 3 doses of MLN9708 specified for the applicable cohort and completed the DLT-assessment period.

Subjects whose treatment with MLN9708 was interrupted or reduced in Cycle 1 for reasons other than DLTs are not eligible for DLT assessment in principle.

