## **8.2 Replacement of Subjects**

Subjects in this study who have not received study treatment may be replaced.

If any major protocol deviation that potentially affects DLT assessment for reasons other than safety concerns as DLT occurs during DLT assessment period, the subject will be excluded from the DLT assessment and additional subjects may be enrolled in this cohort. Additional patients may also be enrolled throughout the study if there seems to be a need for additional data for safety or pharmacokinetics evaluation.

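### The diarrhea exception in DLT criterion 7 states no grade, so a MLN9708-related Grade 4 diarrhea judged controlled is not a DLT under that criterion (narrow gap, one-line fix)

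*Protocol*

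**What the plan says.** Protocol 6.7.3 limits DLTs to events possibly related to MLN9708. Criterion 7 takes in other nonhematologic toxicity of Grade 3 or above and then lists four exceptions. The diarrhea exception is "Diarrhea that is controlled with appropriate supportive care". The exception just before it is "Grade 3 nausea and/or emesis which can be controlled with anti-emetic therapies including anti-emetic prophylaxis". A DLT leads to MLN9708 being interrupted for the rest of that cycle.

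For Cycle 1 dosing in general, 6.3.1 says that "no interruption, delays, or reduction will be permitted". Subjects whose MLN9708 was nevertheless "interrupted or reduced in Cycle 1 for reasons other than DLTs are not eligible for DLT assessment in principle" (6.7.2). Section 3.3 covers a subject who cannot complete MLN9708 in the assessment period "for reasons other than DLTs, the subject will be excluded from the DLT assessment, and additional subject(s) may be enrolled". Section 8.2 provides for exclusion after a major deviation bearing on the DLT assessment "for reasons other than safety concerns as DLT occurs during DLT assessment period".

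From Cycle 2 on, 6.5.1.1.2 says of monotherapy: "For Grade 4 non-hematological toxicities, MLN9708 should be discontinued permanently". Table 6-4 allows a restart with sponsor agreement. For the Rd cohorts, Table 6-9 only asks that permanent discontinuation be considered.

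On adjudication, 6.7.3 states: "The sponsor will consult with the ESEC for the final decision if determination of DLT" or evaluability is difficult. SAP 9.4.2.2 tabulates Cycle 1 DLTs as determined by the safety evaluation committee, and SAP section 10 lists these apart from the investigator's DLTs. The SAP does not restate the DLT definition.

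**The concern.** An exception removes part of what its rule would otherwise catch. Criterion 7 catches Grade 3 and above, so an exception without a grade removes Grade 4 as well as Grade 3. Control cannot be taken to imply Grade 3, because the nausea/emesis exception asks for control and also names Grade 3. That grade would be redundant if control already excluded Grade 4.

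Two things are at stake. DLT incidence in cohorts of 3 to 6 drives the tolerability rule in 6.6.1, where one event changes the outcome. DLT status is also what triggers the explicit hold in Cycle 1; without it, 6.3.1 and 6.5 point to continued full dosing after a Grade 4 drug-related toxicity. Diarrhea is an expected toxicity here: in the weekly single-agent Study C16004 it formed part of a DLT at 2.97 mg/m², the equivalent of the 5.5 mg cohorts (1.4.1, 1.7.4).

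**Working it through.** The plan gives no figure to reproduce: sample size has no statistical rationale (10.2) and no DLT rate is assumed. The check is a reading of the text, then the counting rule, then a range for frequency.

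**1. The four exceptions in criterion 7**

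| Exception | Grade stated | Further condition | Grade 4 event under criterion 7 |
|---|---|---|---|
| Arthralgia/myalgia | 3 or greater | none | exempt, stated in the text |
| Fatigue | 3 or greater | under 7 days | exempt, stated in the text |
| Nausea/emesis | 3 | controlled | DLT |
| Diarrhea | none | controlled | exempt, because no grade is given |

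No other current section of the protocol or SAP puts a grade on the diarrhea exception. What counts as controlled is not defined for diarrhea, whereas anti-emetic prophylaxis is defined.

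**2. Other routes to a DLT for the same event**

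- Criterion 8: Cycle 2 delayed by more than 14 days for lack of recovery.
- Criterion 9: the investigator considers permanent discontinuation necessary.
- Criterion 10, Rd cohorts only: under 80% of planned lenalidomide could be given.
- The committee's determination (6.7.3; SAP 9.4.2.2 and section 10).

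The event remains uncounted only if none of these applies.

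**3. Effect on the 6.6.1 count of one such subject**

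| With a Grade 3 limit | As written, dosing continued | Change in the rule |
|---|---|---|
| 1/3 | 0/3 | enroll 3 more → tolerable |
| 2/3 | 1/3 | intolerable → enroll 3 more |
| 2/6 | 1/6 | sponsor decides with the ESEC → tolerable |

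If the dose is held and the subject is excluded under 6.7.2 and 3.3, the evaluable counts are 0/2, 1/2 and 1/5. After a replacement without a DLT they are again 0/3, 1/3 and 1/6. The held subject's status is not certain, since 6.7.2 speaks only in principle and 8.2 sets safety concerns apart.

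**4. How often**

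The documents give no Grade 4 diarrhea rate. Inputs from Study C16004:

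- Table 1-4: drug-related diarrhea of Grade 3 or higher in 3 of 32.
- Section 1.4.1: two DLTs described as Grade 3 with diarrhea, one at 2.97 and one at 3.95 mg/m².

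Assuming those two are among the three and were never worse than Grade 3, at most 3 − 2 = 1 subject could be Grade 4. So q lies between 0 and 1/32 = 3.1%.

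P(at least one in n) = 1 − (1 − q)^n

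- n = 3, q = 1/32: 1 − (31/32)³ = 1 − 0.909 = 9.1%
- n = 6, q = 1/32: 1 − (31/32)⁶ = 1 − 0.827 = 17.3%
- q = 0: 0% for both

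These overstate the gap. They cover all cycles rather than Cycle 1, include 3.95 mg/m² (3.95 × 1.86 = 7.3 mg, above any dose here), and ignore the routes in step 2. Section 1.7.4 reports no Grade 3 or higher events at the 4.0 mg equivalent and mentions only Grade 3 events, in 2 of 6, at the 5.5 mg equivalent.

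**The case against.** The strongest reply is that the gap hardly matters in practice. The documents report no Grade 4 diarrhea. SAP 9.4.2.2 points to a committee-determined DLT count, and 3.1 has the sponsor weigh all safety data, with transition discretionary even after a tolerable result. The design also already exempts Grade 4 arthralgia/myalgia and short fatigue, so exempting controlled diarrhea across all grades could be a coherent choice.

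Most of this stands and sets the weight of the point. It does not remove the gap. Consultation in 6.7.3 is for difficult cases, and an exemption that reads plainly may not look difficult. The Grade 4 exemptions for arthralgia and fatigue are explicit, and the closest comparator, the other gastrointestinal exception conditioned on control, stops at Grade 3.

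Several stronger readings are tempting but not supported:

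- **A controlled Grade 4 diarrhea can never be a DLT.** Criteria 8 to 10 and the committee can still make it one.
- **The subject must stay on drug in Cycle 1.** Section 8.1 lists adverse events as a reason for removal and 9.2 leaves that to the investigator. If permanent discontinuation is required, criterion 9 applies.
- **The exemption contradicts the Grade 4 stopping rule throughout.** That rule starts in Cycle 2 and is firm only for monotherapy; Table 6-9 is weaker for the two Rd cohorts. An investigator who applied it in Cycle 1 would trigger criterion 9.
- **3 of 32 is a Grade 4 rate.** Section 1.4.1 describes two diarrhea DLTs in that study as Grade 3.
- **The version 2.2 change memo, which shows a Grade 3 limit, proves a drafting error.** A change memo describes superseded text. The point rests on current 6.7.3 alone.

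**Conclusion.** The point holds as a narrow defect in a stated rule. The uncounted case is a related Grade 4 diarrhea that is judged controlled, does not lead to permanent discontinuation, recovers in time for Cycle 2, is compatible with at least 80% of lenalidomide in the Rd cohorts, and is not brought in by the committee. It would still appear in the by-grade adverse event tables, so what is lost is its place in the DLT count and the automatic Cycle 1 hold.

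The literal reading needs no assumption. The frequency range does: it depends on how the three C16004 cases are graded and on carrying over a rate from 32 overseas subjects. Minor severity; a cheap improvement to a definition that feeds a primary endpoint.

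**What to change.** In criterion 7 of 6.7.3, put the words Grade 3 in front of "Diarrhea that is controlled with appropriate supportive care". Any MLN9708-related Grade 4 diarrhea is then a DLT, as Grade 4 nausea/emesis already is, and the Cycle 1 hold follows.

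The cost is one grade in one line, with no new procedures or data. The DLT count may be slightly less favourable, and one extra DLT among the first 3 subjects would call on the 3-subject expansion already in the plan.

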## **6.8 Permitted Concomitant Medications and Procedures**

Throughout the study, investigators may prescribe any concomitant medications or perform procedures deemed necessary to provide adequate supportive care except for those listed in "[6.9 Excluded Concomitant Medications and Procedures](#)

## **6.9 Excluded Concomitant Medications and Procedures**

The following medications and procedures are prohibited during the study.

- Systemic treatment with strong inhibitors of CYP3A inducers (rifampicin, rifabutin, carbamazepine, phenytoin, phenobarbital), or use/ intake of foods containing St. John's Wort during the study.
- Any antineoplastic treatment other than Rd administered concomitantly with MLN9708 in the Rd combination cohort. Treatment with corticosteroids 10 mg of prednisolone per day or less is permitted.
- Radiotherapy (note that, in general, the requirement for local radiation therapy indicates disease progression).
- Myeloid growth factors (e.g., G-CSF, granulocyte macrophage-colony stimulating factor [GM-CSF] is not permitted in Cycle 1 unless Grade 4 neutropenia occurs. Their use should follow published guidelines and/or institutional practice, however, alternative usage may be reviewed with the Millennium clinician or study clinician designee.
- Platelet transfusions to help patients meet eligibility criteria of ANC and platelet counts are not allowed prior to MLN9708 dosing on Cycle 1 Day 1 (within 7 days before the test).

## **7. STUDY PROCEDURES**

MLN9708 treatment must be initiated within 7 days after the enrollment. Refer to [Appendix A](#) for an outline of procedures required at each visit.

### **7.1 Subject Screening**

Before any protocol-specified procedure, all subjects must sign and date the informed consent form.

The investigator will be expected to create and maintain a screening log for all potential study candidates that includes information about the potential candidate (sex, date of birth), date, and outcome of the screening process (e.g., enrollment into study, reason for ineligibility or refused to participate).

All existing test results (e.g., HIV, hepatitis B virus [HBV], HCV), diagnostic imaging results (e.g., X-ray, CT, MRI) and bone marrow test results, for example, obtained prior to the date of consent acquisition may be used as data at the time of screening, provided the subject's consent is obtained.

### **7.2 Examinations, observations, and evaluations**

The investigator will conduct examinations, observations, and evaluations of the subject according to the following procedures from the informed consent until the end of treatment visit. The subject assessments/observations will all be performed by the same investigator, in principle.

#### **7.2.1 Screening period**

All of the following exams, observations, and evaluations will be performed within 28 days before first dose, unless otherwise specified. Subjects meeting all of the eligibility criteria specified in "[4 SUBJECT ELIGIBILITY](#)" prior to subject enrollment will be enrolled to this study in accordance with Section [5 "SUBJECT ENROLLMENT."](#)

- Informed consent
- Assessment of eligibility, according to the inclusion/exclusion criteria

- Subject background (including medical history, concomitant disease, details of multiple myeloma diagnosis [date of diagnosis, histological type, current clinical stage] (see [Appendix H](#)), history of prior-treatment for multiple myeloma [chemotherapy, radiotherapy, transplantation, surgery])
  - For past medical history, the following clinically significant diseases and procedures that have resolved or ended before the initial dose.
    1. Diseases listed in the exclusion criteria (all such diseases that have resolved or ended prior to enrollment)
    2. Diseases or procedures experienced by the patient in the last 3 months other than those described in #1, except for transient diseases (e.g., upper respiratory tract inflammation, cold, headache)
    3. Other diseases that could affect the MLN9708 evaluation
  - "Concomitant disease" refers to any symptoms or diseases being experienced by the subject at the time of the first study treatment, and includes all clinically significant laboratory tests, 12-lead ECGs, and physical examination finding abnormalities. Concurrent illnesses will be investigated in detail (and diagnosis terms obtained wherever possible).
- ECOG performance status (see [Appendix B](#))
- Vital signs (sitting blood pressure, pulse rate and axillary temperature, and transcutaneous oxygen saturation [SpO2])
- Height, weight
- 12-lead ECG (QRS, QT, QTc, PR and heart rate)
  - The 12-lead ECG is performed with the subject at rest in a supine position.
- Laboratory tests: See [Table 7-1](#) for the test parameters.
  - Hematology tests
  - Chemistry tests
  - Urinalysis
  - Virus tests (HIV antibody, HBs antigen, HCV antibody. The test results will not be recorded in the eCRF.)
  - $\beta$ 2-microglobulin
  - Immunoglobulin quantitation (IgG, IgM, IgA, IgD)
  - FLC
- Serum M-protein (protein fraction test by electrophoresis; immunofixation)
- Urine M-protein by 24-hour urine collection (protein fraction test by electrophoresis; immunofixation)
- Pregnancy test (serum or urine; only if the subject is of childbearing potential)
- Serious adverse events (see “[9.1.1 Adverse Events](#)” through “[9.3 Serious Adverse Event Reporting Procedures](#)”)

- X-rays
  - Chest
  - Bone (head, cervical vertebrae, thoracic vertebrae, lumbar vertebrae, pelvis, both upper arms, both forearms, both femurs, both lower legs); in two directions for each, except for the pelvis
  - If bone X-ray is performed within 8 weeks before the first dose, the X-ray results may be used as screening data.
- CT/MRI (chest, abdomen)
  - Unless a patient shows hypersensitivity to contrast or concern for potential aggravation of renal dysfunction, all CT/MRI should be performed with contrast.
  - When CT/MRI scan is performed within 8 weeks before the first dose of MLN9708, it may be used as screening data.
- Bone marrow aspirate: Percentage of plasma cells in bone marrow (Note: When collecting the sample, anatomical locations that are irradiated in the past should be avoided.)

### **7.2.2 Treatment period**

Study treatment must be initiated within 7 days after enrollment. If study treatment cannot be initiated within 7 days, the patient may be rescreened after obtaining additional informed consent. For details, see “[5 SUBJECT ENROLLMENT](#).” Hospitalization is generally required from the first dose of MLN9708 through the start of Cycle 2. However, if a subject wishes to return home temporarily and the investigator confirms that the subject’s symptoms are stable based on the available data collected in the study to that point, then the subject may return home temporarily, provided this does not interfere with the study observations/tests.

See “[6.3 Dosage, administration method, dosing schedule](#)” for more details on the administration of MLN9708 and Rd. Unless otherwise specified, the following procedures must be followed before administering MLN9708 in each cycle. See [Appendix A](#) for the acceptable test, observation, and examination time windows.

- Obtaining informed consent to extended treatment
  - Written consent to the extended administration of MLN9708 will be obtained prior to Cycle 2 treatment from subjects who meet the criteria specified in “[6.4 Criteria for Beginning the Next Cycle of Treatment](#)” and who have experienced no safety concerns.

- Medical interview (including confirmation of treatment compliance): Day 1 of each Cycle
- ECOG performance status: See [Appendix B](#)
  - Cycle 1: Days 1, 8, and 15
  - Cycles 2 and subsequent cycles: Day 1
- Vital signs (sitting blood pressure, pulse rate and axillary temperature, SpO2)
  - Cycle 1: Days 1, 8 and 15
  - Cycles 2 to 12: Days 1 and 15
  - Cycle 13 and subsequent cycles: Day 1
- Body weight
  - Cycle 1: Before MLN9708 dosing on Day 1. If a patient's body weight at screening is measured within 3 days before the first dose, then this measurement may be used for the Cycle 1 Day 1 data.
  - Cycle 2 and subsequent cycles: Day 1 of each cycle. Measurements taken within 3 days before dosing will be accepted.
- 12-lead ECG (QRS, QT, QTc, PR and heart rate)
  - Day 1 of Cycle 1: Before dosing
  - Day 15 of Cycle 1: Before dosing, 30 minutes ( $\pm$  10 min) after dosing, 1 hour ( $\pm$  15 min) after dosing, and 4 hours ( $\pm$  45 min) after dosing
  - Day 16 of Cycle 1: 24 hours ( $\pm$  1 hr) after dosing on Day 15
- Laboratory tests: See [Table 7-1](#) for the test parameters.
  - Hematology tests
    - Cycle 1: Days 1, 8, 15 and 22
    - Cycles 2 and 3: Days 1, 8 and 15
    - Cycles 4 to 12: Days 1 and 15
    - Cycle 13 and subsequent cycles: Day 1

If a screening test is performed within 3 days before the first dose, the results may be used as the Cycle 1 Day 1 data.
  - Chemistry tests
    - Cycle 1: Days 1, 8, 15 and 22
    - Cycles 2 and 3: Days 1, 8 and 15
    - Cycles 4 to 12: Days 1 and 15
    - Cycle 13 and subsequent cycles: Day 1

If a screening test is performed within 3 days before the first dose, the result may be used as the data as Cycle 1 Day 1 data. Hemoglobin A1c (HbA1c) will be measured only on Day 1 of each cycle.

- Urinalysis: Day 1 of each cycle
- Immunoglobulin quantitation (IgG, IgM, IgA, IgD): Day 1 of each cycle
- FLC: FLC will be measured as appropriate if a response assessment requires confirmation or disease progression is suspected (see [Appendix G](#)).
- Serum M-protein (electrophoresis protein fraction test): Performed on Day 1 of each cycle. If a screening test is performed within 7 days before the first dose, the results may be used as the Cycle 1 Day 1 data.
- Urine M-protein (electrophoresis protein fraction test):

**Subjects whose urine M-protein is detected only in urine at screening**

- Measurement by 24-hour urine collection
  - Urine samples will be collected prior to MLN9708 dosing on Cycle 1 Day 1. If a screening test is performed within 7 days before the first dose, the results may be used as the Cycle 1 Day 1 data.
  - Samples will be collected every 2 cycles prior to MLN9708 dosing on Day 1 of Cycles 3 and subsequent cycles (Cycles 3, 5, 7, 9, 11 and on [odd-numbered cycles]). It will be acceptable to collect samples between Days 23 and 28 of the preceding cycle.
- Measurement by casual urine
  - Samples will be collected every 2 cycles prior to MLN9708 dosing on Day 1 of Cycles 2 and subsequent cycles (Cycles 2, 4, 6, 8, 10, 12 and on [even-numbered cycles]).

